1.3 SCHEDULE OF ACTIVITIES

Summary of Variables, Measurement, and Data Collection Time Points			
Variables and Measurement	0	6	12
Feasibility			
*Process evaluation checklist (bi-monthly)	--	--	--
*Screening and enrollment logs	X	X	X
*Intervention attendance	X	X	X
*Data collection attendance	X	X	X
Exit interview			X
Biological CVD Risk Factors (Primary Outcomes)			
Systolic and diastolic blood pressure	X	X	X
Fasting blood glucose	X		X
Fasting lipid profile	X		X
Arterial stiffness (carotid-femoral PWV)	X		X
	X		X
Health Behavior (Secondary Outcomes)			
Nutrition and food security	X	X	X
Physical activity questionnaire	X	X	X
Accelerometer (7 days, 24 hours/day)	X	X	X
Sleep questionnaire	X	X	X
Perceived stress	X	X	X
Coping response inventory	X	X	X
Eating self-efficacy scale	X	X	X
Exercise self-efficacy scale	X	X	X
Biological Influences (Secondary Outcomes)			
Height, Weight, BMI	X	X	X
Waist Circumference	X	X	X
Hair Cortisol and Hs-CRP	X		X
Vasomotor symptoms questionnaire	X	X	X
Demographic, Sociocultural, and Environmental			
Demographic questionnaire (e.g., age, education)	X	X	X
Acculturation questionnaire (e.g., years in US)			
Everyday discrimination scale			
Brief resilience scale			
Health history questionnaire			
Reproductive history questionnaire			
Community food assessment			
Neighborhood risk assessment			
Physical activity resource assessment			

0 = baseline; 6 = 6-month (completion of intensive intervention and continued support); 12 = 12-month (after 6 months of maintenance on own); BMI = body mass index; Hs-CRP = high-sensitivity C-reactive protein; PWV = pulse wave velocity

*Completed by Project Manager

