Data will be collected at Time 1 (baseline [0 months]), Time 2 (post Intensive Intervention and Continued Support [6 months]), and Time 3 (6 months after completion of Continued Support [12 months]). Data collected will include the primary outcomes of blood pressure, arterial stiffness based on carotid-femoral pulse wave velocity measures, lipid profile (total cholesterol, high-density lipoprotein, low-density lipoprotein, triglycerides), blood glucose; secondary outcomes of health behaviors (Sleep Quality Questionnaire, Food Behavior Checklist, Physical Activity Questionnaire, and 7-day Accelerometer), self-efficacy (Eating Self-Efficacy Scale and Exercise Self-Efficacy Scale), body mass index, waist circumference, hs-CRP, hair cortisol, and vasomotor symptoms. We will also evaluate the feasibility of the study including, number of eligible participants; methods of identifying/recruiting participants; willingness of participants to be randomized; practicality of delivering the intervention in the proposed setting; enrollment and retention rates, and suitability of the intervention and assessment protocol. Data analysis will use descriptive statistics and general linear mixed models to test the hypotheses. Both intervention and control group participants will each receive \$120 for their time during data collection visits (\$35 at Time 1, \$40 at Time 2, \$45 at Time 3) and \$5 to help with transportation costs each time they come to class or data collection visit.

Participants in the intervention group will receive a 12-week Intensive Intervention (Phase I) with weekly 2-hour sessions consisting of 60 minutes of nutrition and exercise education and coping skills training, a 45-minute physical activity class, and 15-minute stress management session. During Continued Support (Phase II), participants will meet monthly for 3 months for 60 minutes of classroom discussion regarding problems they are having with nutrition and physical activity. Data collection in the wait-list control group will occur at the same time intervals as women in the intervention group. Following the last data collection, we will offer Phase I of the intervention to women in the wait-list control group.

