4 STUDY DESIGN

4.1 OVERALL DESIGN

This study will use a cluster randomized repeated measures study design with two groups to evaluate the feasibility and initial efficacy of the intervention with 80 perimenopausal Latinas. The intervention group (n=40) will receive a 3-phased intervention. In Phase I (Intensive Intervention), bilingual community health workers will meet with women in small groups to deliver 12 weekly (3 months) 2-hour sessions including education, group physical activity, stress management, and coping skills training. Phase II (Continued Support) consists of 3 monthly 1-hour sessions led by community health workers to problem-solve issues related to nutrition and exercise, stress management, and to provide feedback and support. During Phase III (Follow-up), participants are expected to maintain skills on their own for 6 months. Data will be collected at baseline (Time 1), completion of Phase II (Time 2, 6 months after baseline), and after completion of 6 months on their own (Time 3, 12 months after baseline). Data in the wait-list control group (n=40) will be collected at the same time intervals as the intervention group. After Time 3 data collection, they will be offered the Intensive Intervention (12 weekly sessions). Both groups will receive reminders a week prior to each data collection visit and a monthly "thank you" card for their continued participation.

Data will be collected at Time 1 (0 months [baseline]), Time 2 (6 months [completion of the intervention]) and Time 3 (12 months [after 6 months with no contact from the study staff]). Time 2 data will determine the magnitude of the intervention effects after the intensive intervention and continued support; Time 3 data collection will test initial efficacy after participants have had sufficient time to implement their new nutrition, physical activity, and coping skills on their own. We will assess feasibility using questionnaires at Time 3, as well as process evaluations and attendance logs. We chose these times because 6-to-12 months after completion of an intervention is a standard interval for follow-up in behavioral interventions during perimenopause [34].

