6 STUDY INTERVENTION(S) OR EXPERIMENTAL MANIPULATION(S)

6.1 STUDY INTERVENTION(S) OR EXPERIMENTAL MANIPULATION(S) ADMINISTRATION

6.1.1 STUDY INTERVENTION OR EXPERIMENTAL MANIPULATION DESCRIPTION

Intensive Intervention

The intensive intervention consists of 12 weekly bilingual (English, Spanish) sessions that include 60 minutes of interactive learning, 45 minutes of physical activity, and a 15-minute stress management session. The first 8 sessions will integrate education from SCSV related to CVD risk awareness, healthy food choices, physical activity, blood pressure control, and diabetes. To enhance the relevance of the curriculum to perimenopause, we will include messages from American Heart Association Go Red Por Tu Corazón. Each week CHWs will give participants a SCSV or AHA Go Red Por Tu Corazón handout with information on healthier meals and increasing daily physical activity. In the remaining four learning sessions of Phase I, we will integrate previously tested and acceptable coping skills training sessions (i.e., goal-setting, problem-solving, cognitive restructuring, conflict resolution, assertiveness training) with a focus on barriers for perimenopausal Latinas. Trained bilingual CHWs will deliver learning sessions and 15-minute stress management sessions in groups of 20 participants.

Physical activity classes will be held for 45 minutes after the intensive intervention classes and will include a warm-up and then activities such as Zumba, Kick Boxing, walking, use of light weights and stretch bands, and a cool-down. A bilingual physical activity interventionist certified by the American College of Sports Medicine will teach the physical activity classes and reinforce ways to increase physical activity and decrease sedentary behaviors. At baseline, we will give participants an accelerometer and the RA will train them in its use as part of the intervention. The intervention group will be encouraged to increase their physical activity weekly by small increments until they are averaging 10,000 steps a day or 150 minutes per week; this group will also be provided information on the sociocultural and built environments such as a list of grocers where they can access healthy affordable food and free or low-cost spaces to exercise (e.g., YWCA/YMCA) close to home. Missed physical activity sessions will not be made up, but participants can make up learning and stress management sessions.

Continued Support

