During Continued Support, participants will return to the church for classes once a month for 3 months. As a part of the intervention, participants engage in a discussion run by the bilingual CHW, who will help women solve problems they have encountered related to nutrition and physical activity for 60 minutes and then receive a 45 minute physical activity class and 15-minute stress management session. If a participant misses a class, the bilingual interventionist will call and ask how the woman doing and give the date of the next class. Continued support classes will not be made up.

Wait-List Control Group

Data will be collected from the wait-list control group at Time 1, Time 2, and Time 3; and participants will receive up to \$120 for their participations (\$35 at Time 1, \$40 at Time 2, and \$45 at Time 3) in addition to a \$5 transportation voucher at each data collection. The wait-list control group will receive a "thank you" postcard for their continued participation. Participants will receive a accelerometer and log book after they have completed Time 3 data. At that time, the wait-list control group (the cluster) will also be offered the intervention classes in the church. In addition the monthly "thank you" cards, participants will be called several days before classes and data collection to remind them.

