6.3 MEASURES TO MINIMIZE BIAS: RANDOMIZATION AND BLINDING

After enrollment and baseline assessment, the two churches will be randomized to either the intervention or wait-list control group using a computer-generated randomization table. Participants will be informed of their group assignment by telephone. Data collection research assistants will be blinded to group status.

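### The accelerometer serves as both outcome measure and intervention component, and issuing it at baseline as part of the intervention contradicts randomizing the churches after baseline.

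*Combined protocol and SAP*

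**What the plan says.** **Outcome use.** The Section 1.3 schedule has a row "Accelerometer (7 days, 24 hours/day", marked at 0, 6 and 12 months with no restriction by arm, and Section 8.1 repeats it. Section 2.3.1 names the device among the "secondary outcomes of health behaviors (Sleep Quality Questionnaire, Food Behavior Checklist, Physical Activity Questionnaire, and 7-day Accelerometer". For controls, Section 4.1 states "Data in the wait-list control group (n=40) will be collected at the same time intervals as the intervention group".

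**Intervention use.** Under Intensive Intervention, Section 6.1.1 says that at baseline "we will give participants an accelerometer and the RA will train them in its use as part of the intervention". The next sentence sets the intervention group a goal of 10,000 daily steps or 150 weekly minutes. In Section 6.2.1, community health workers discuss daily step counts at the continued-support sessions.

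**Controls' device.** Under Wait-List Control Group, Section 6.1.1 says "Participants will receive a accelerometer and log book after they have completed Time 3 data". It then offers that cluster the classes.

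**Order of events.** Section 6.3 says "After enrollment and baseline assessment, the two churches will be randomized", and Section 2.3.1 gives the same order. Section 6.3 also keeps the data-collection research assistants blinded to group.

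**The concern.** Physical activity is a behaviour the programme sets out to change, and the accelerometer is the only device-based measure of it; the other is a questionnaire. An outcome instrument should be applied identically in both arms, and a baseline should be recorded before any intervention begins. A device issued at baseline, with training that belongs to the intervention, puts both conditions in doubt.

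Three things are at stake: whether the baseline week reflects usual activity, whether controls are exposed to a component meant to be withheld until after Time 3, and whether the two arms are recorded under the same conditions at 6 and 12 months. Feasibility is a primary objective and includes the suitability of procedures and outcome measures, so a measurement procedure that field staff cannot follow unambiguously also matters in its own right.

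**Working it through.** The plan gives no figure for this point, so the check sets the passages side by side.

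1. **Hand-out against randomization.** The hand-out is at baseline (6.1.1). Churches are randomized after baseline assessment (6.3, 2.3.1), and women learn their group by telephone afterwards. A hand-out at baseline therefore cannot be limited to the intervention arm. Either all 80 women receive it, including the 40 who become controls, or it does not happen at baseline. The two sections cannot both be followed with the component confined to one arm.

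2. **Hand-out against the baseline recording.** The baseline visit takes about 90 minutes (5.5). The recording takes 7 × 24 = 168 hours, so it must run on beyond the visit. If device and training are given at that visit, which is the plain sense of the sentence, the whole baseline week is recorded after an intervention component has begun. This assumes that the hand-out does not wait until the wear week is over; the documents do not say.

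3. **Controls' device against the schedules.** Control data are due at all three times (1.3, 8.1, 2.3.1, 4.1, 6.1.1), yet controls are given a device after Time 3. These statements fit together if there are two devices, or if the measuring device is lent and returned. The documents state neither, and do not say whether the wearer can see the readout.

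4. **Effect on the comparison.** Section 9.4.1 compares change between the groups. Let r be the extra activity recorded in a wear week only because of the recording conditions (visible counts, training, more complete wear), with I for intervention and C for control. Then

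   observed difference in change = true difference + (r_I − r_C at follow-up) − (r_I − r_C at baseline).

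   - Same device, instructions and masking in both arms: both brackets are zero if the arms react alike.
   - All women are trained on a visible device at baseline, and only the intervention arm keeps using it: the baseline bracket is about zero, although both baselines may be raised. The follow-up bracket can be non-zero.
   - All women are trained at baseline and keep the device: the brackets may cancel, but up to 40 controls have received a programme component and the true difference shrinks.
   - Only intervention women are trained, early enough to affect baseline wear: the baseline bracket is positive if r_I exceeds r_C, and the gain is understated.

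   The direction of bias therefore depends on details the plan leaves open. The documents give no value for r, so its size cannot be computed.

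5. **Who does the training.** A research assistant trains women in the device as part of the intervention (6.1.1), while data-collection research assistants are blinded (6.3). The documents do not say that these are different people.

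**The case against.** A reader might infer that controls have no accelerometer until after Time 3, so that no between-arm comparison exists. The documents do not support this. The wait-list sentence does not say that this is the controls' first or only device, and does not call it the outcome instrument. It pairs the device with a log book and is followed by the offer of classes, which fits a delayed programme item. The same paragraph opens with "Data will be collected from the wait-list control group at Time 1, Time 2, and Time 3", and both schedules mark the accelerometer at all three times without regard to arm.

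A reader might also infer that any effect of device feedback confounds the result. That goes too far. The trial tests a multi-component package; lasting activity produced by self-monitoring is part of the programme's effect. Only differences confined to the recording itself are bias.

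The hand-out sentence sits under Intensive Intervention, so its participants may well be meant as intervention women only. That is a fair reading of intent and weakens the case that controls will in fact be exposed. It does not remove the timing conflict, because those women cannot be identified at baseline.

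Finally, the consequence is limited. Accelerometry is one measure of a secondary outcome, a physical activity questionnaire is scheduled at the same three times, and Section 9.1 says the pilot is not expected to test the main trial's hypotheses. This stands and is reflected in the severity.

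**Conclusion.** The timing contradiction is established from the text: an intervention component is issued at baseline, when no arm has been assigned. On a literal reading it reaches all 80 women, 40 of them future controls, and affects the baseline activity week if the hand-out coincides with the start of wear.

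The further risk, that the arms differ in familiarity, self-monitoring and wear during outcome recording, is conditional. It requires one device, or one kind of device, with a visible readout to serve both purposes. The step goal and the discussion of step counts make a visible readout plausible; nothing confirms or excludes it.

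The accelerometer comparison remains available, with up to 40 women per arm before attrition. Severity is low to moderate: the flaw is real and easily removed, and is confined to one secondary outcome measure in a pilot.

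**What to change.** Reconcile Sections 1.3, 6.1.1 (both subsections), 6.3 and 8.1 so that the two uses are separate.

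1. **Outcome measurement.** Both arms wear the same device under the same instructions for 7 days at 0, 6 and 12 months, with no display or feedback, and return it after each wear.
2. **Self-monitoring.** The programme device and its training go to the intervention arm only after baseline wear is complete and the churches have been randomized. Staff who are not the blinded data collectors issue it. Controls receive theirs after Time 3, as already planned.

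The cost is protocol wording and at most a small pool of outcome devices that rotate between women. At the planned enrollment of 8 to 10 women a week (5.5), about 10 devices are in use at a time, or about 20 if return and reset take a further week. That turnaround is an assumption, as is follow-up spaced like enrollment; visits bunched together would need more. If baseline assessment was not already meant to include the wear week, randomization waits up to 7 days after the last baseline visit. The programme itself loses nothing.

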6.1.2 ADMINISTRATION AND/OR DOSING

See 6.1.1 for details

6.2 FIDELITY

6.2.1 INTERVENTIONIST TRAINING AND TRACKING

Fidelity of the Intervention

We have structured the fidelity of the intervention using the NIH five category Treatment Fidelity Framework [44]. For category one, **treatment design**, the intervention and control group condition is clearly defined and participants will receive the same duration of contact over time. The CHWs will have experience teaching health interventions, and the theoretical model is clearly articulated. For category two, **training**, The bilingual interventionists will be trained by the PI using a standardized manual and teach back the intervention to the PI. For category three, **delivery**, the bilingual project coordinator will observe two randomly selected sessions per month using a checklist to score delivery based on pre-identified content. We define fidelity as delivering >80% of the protocol content. If drift occurs, the PI will retrain CHWs until the protocol is followed consistently. CHWs will collect data on attendance, reasons for absence, and make-up learning sessions provided. For category four, **receipt**, interventionists will ask questions and generate discussion during each learning sessions to assess the degree to which participants understand the content and participants will be asked to set a goal based on the information reviewed during the learning session. CHWs will evaluate category five, **enactment**, during the 3 monthly continued support sessions by discussing changes in diet, physical activity, number of steps taken per day, and stress management; RAs will also assess enactment during exit interviews at Time 3 with participants.

6.3 MEASURES TO MINIMIZE BIAS: RANDOMIZATION AND BLINDING

After enrollment and baseline assessment, the two churches will be randomized to either the intervention or wait-list control group using a computer-generated randomization table. Participants will be informed of their group assignment by telephone. Data collection research assistants will be blinded to group status.

6.4 STUDY INTERVENTION/EXPERIMENTAL MANIPULATION ADHERENCE

See 6.2.1 for details

6.5 CONCOMITANT THERAPY

N/A

6.5.1 RESCUE THERAPY

N/A

7 STUDY INTERVENTION/EXPERIMENTAL MANIPULATION DISCONTINUATION AND PARTICIPANT DISCONTINUATION/WITHDRAWAL

7.1 DISCONTINUATION OF STUDY INTERVENTION/EXPERIMENTAL MANIPULATION

The intervention will only be discontinued after consultation with the study team and the program officer.

7.2 PARTICIPANT DISCONTINUATION/WITHDRAWAL FROM THE STUDY

Participants are free to withdraw from participation in the study at any time upon request.

An investigator may discontinue a participant from the study for lost-to-follow up and unable to contact subject.

The reason for participant discontinuation or withdrawal from the study will be recorded. Participants who sign the informed consent form and are randomized but do not receive the study intervention may be replaced. Subjects who sign the informed consent form, and are randomized and receive the study intervention, and subsequently withdraw, or are discontinued from the study will not be replaced.

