Phase* or Stage: Cluster randomized controlled with an experimental and wait-list control group.

Description of Sites/Facilities Participants recruited from community sites in Durham, Wake, Orange, Alamance, and Lee Counties in North Carolina.

Enrolling Participants:

Description of Study Intervention/Experimental Manipulation: An experimental group of women receive an intervention consisting of *Su Corzaón Su Vida* education sessions, group physical activity, stress management, and coping skills training. The wait-list control group is offered the intervention at the end of Time 3 (12 months).

[figure not shown]
Manipulation:

Study Duration*: A total of 4 years or 48 months.

Participant Duration: Each participant will be in the study a total of 12 months.

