2.3 RISK/BENEFIT ASSESSMENT

2.3.1 KNOWN POTENTIAL RISKS

Risks to Human Subjects

Institutional Review Board (IRB) approval was obtained from The University of North Carolina at Chapel Hill (UNC-CH). Using a cluster randomized two-group, repeated measures experimental design, the goal of the study is to investigate the feasibility and initial efficacy of a 12-month intervention consisting of: **Phase I**) 12-week nutrition and exercise education, physical activity group sessions, coping skills training, and stress management intervention in perimenopausal Latinas; **Phase II**) 6 months of continued monthly contact to help women improve health behaviors and self-efficacy; and **Phase III**) 6 months of health maintenance without contact from study staff. We will partner with community centers to enroll women and we will partner with two churches in two North Carolina counties to deliver the intervention.

Inclusion criteria include age 40-60 years; self-identify as Latina; understand spoken English or Spanish; perimenopausal (menstrual bleeding in the past three months, but timing of periods have varied in past year, or no menstrual bleeding in the past 3-11 months) or early postmenopausal (1-2 years since final menstrual period); intact uterus and at least one ovary; not currently pregnant; no hormone therapy or oral contraceptives in the past three months. Potential participants will fill out a health history questionnaire to ascertain if they have a history of CVD (heart attack, stroke, coronary heart disease), heart murmur, congenital heart disease, family history of sudden death, difficulty walking or exercising. Women who answers yes to any of these health history questions will be excluded from the study and referred to a health care provider. After enrollment and baseline assessment, two churches in two counties will be randomly assigned to either the intervention or control group. Participants will be assigned to the group in their respective county. Participants will be informed of their group assignment by telephone.

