Subject Accrual and Compliance with Inclusion/Exclusion. All data from participants screened for the study will be entered into the REDCap electronic study database. Designated research staff will collect, gather, and enter required data (written informed consent, Health Insurance Portability and Accountability Act (HIPAA) authorization, medical history and demographics) onto study data forms. Screened patients who do not meet study eligibility will have specific screening data entered into the study database. The collected data will be helpful in examining the patient population and feasibility of enrollment criteria and will include gender, age, race and reason for exclusion. All dates will be shifted and other Personal Health Information (PHI) will be removed from the study database upon study completion.

Participant Compliance to the Intervention. Data on compliance to the intervention will be collected weekly by the senior RA and reviewed quarterly by the Co-Mentors, scientific advisors, the Senior RA, Safety Officer, and PI. Compliance on the part of participants will be evaluated by attendance and process evaluation as outlined in the study. If intervention attendance drops below 80%, participants who have stopped coming will be called to ask for feedback. Using information gained from these phone interviews, the PI will schedule a meeting with the Co-mentors, scientific advisors, and the Safety Officer to discuss methods for improving compliance.

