9.3 POPULATIONS FOR ANALYSES

Means, standard deviations, minimums, medians, and maximums will be determined for each continuous variable; frequencies and percentages will be tabulated for each categorical variable. Preliminary analyses will be performed to determine whether, despite randomization, the intervention and control groups were unbalanced on age, education, income, or other participant characteristics. Any variable with an imbalance between the groups at baseline will be examined to determine whether it is related to any of the outcome variables. If significant relationships are identified, the variable will be included as a covariate in the models for the affected outcome(s) as a potential confounder. An intent-to-treat analysis will be used in which all subjects are included in the analysis and analyzed according to their initial randomized assignment.

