9.4 STATISTICAL ANALYSES

9.4.1 GENERAL APPROACH

Aim 1. Using descriptive statistics (e.g., frequency, percentage, means, SDs), we will summarize enrollment and retention rates, and proportion of intervention sessions the participants attended. We will measure fidelity of the intervention ($\geq 80\%$ attendance; delivery of $>80\%$ of content) using the process evaluation guide, and assess participant satisfaction with the study and the intervention using the exit interview.

Aim 2. We will use an intent-to-treat approach. Because random assignment is by group and not individually, we will examine potential systematic differences closely between the two groups, comparing baseline characteristics using the Student's t-test or Mann-Whitney test for continuous variables and Chi-square or Fisher's exact test for categorical variables. We will assess change in primary and secondary outcomes in the intervention and control group using the Student's t-test or Mann-Whitney test for continuous variables and Chi-square or Fisher's exact test for categorical variables.

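### Section 7.2 allows women to be replaced after the churches are randomised, so a replacement is recruited into an arm that is already fixed

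*Combined protocol and SAP*

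**What the plan says.** All references are to the combined protocol and SAP.

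- **Replacement (7.2).** "Participants who sign the informed consent form and are randomized but do not receive the study intervention may be replaced". The same section rules out replacing a woman who has received the intervention and then leaves.
- **Order and unit of randomisation (6.3).** "After enrollment and baseline assessment, the two churches will be randomized to either the intervention or wait-list control group". Women then learn their group by telephone. Section 2.3.1 gives the same order and adds: "Participants will be assigned to the group in their respective county". No second randomisation is described.
- **Blinding (6.3).** "Data collection research assistants will be blinded to group status". No other role is said to be blinded. Recruitment is by a community health worker and a research assistant (5.5), and community health workers deliver the classes (6.1.1). The documents do not say whether these are the same people.
- **Wait-list arm (1.1, 4.1).** These women are offered the classes only after the 12-month visit.
- **Analysis set (9.3).** Under intent-to-treat, "all subjects are included in the analysis and analyzed according to their initial randomized assignment". Section 9.4.1 repeats intent-to-treat for Aim 2.
- **Feasibility measures.** Attendance and retention are among the primary outcomes in section 3. For Aim 1, "we will summarize enrollment and retention rates, and proportion of intervention sessions the participants attended" (9.4.1), with attendance of at least 80% given as a fidelity mark. Section 8.3.3.2 adds an action trigger: "If intervention attendance drops below 80%, participants who have stopped coming will be called to ask for feedback".

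No section says how a replaced woman, or the woman who takes her place, is counted.

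**The concern.** In a trial that allocates whole churches, enrolling and assessing every woman before the churches are randomised prevents knowledge of the arm from influencing who joins. The plan adopts that order, and section 7.2 then makes an exception to it. A woman can be randomised and fail to receive the intervention only after randomisation. Her replacement therefore has to be found, consented and assessed when her church's arm is settled and existing participants have been told theirs. Nothing in the plan keeps the arm from the people who recruit her.

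Blinded data collection protects how women are measured. It does not protect which women enter. A recruiter filling an empty class place could favour women who seem likely to attend, and a woman who knows that she would get the classes at once may differ from one who agreed to either arm.

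The second problem is one of fit. Section 9.3 ties analysis to the initial randomised assignment, but a replacement was not in the study when that assignment was made. The plan does not say whether she is added, substituted or set aside.

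**Working it through.** **1. Does the order of events force late entry?**

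- Replacement requires that the woman has been randomised (7.2).
- Randomisation is a single event for two churches, after enrolment and baseline (6.3).
- Arm follows county (2.3.1).

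Every replacement under 7.2 therefore enters after allocation, with her arm known in advance. This follows from the text and needs no assumption.

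**2. Which arm is affected?** Read sensibly, the rule concerns women who never start classes, so it acts mainly in the intervention arm. Read literally, no wait-list woman receives the intervention before Time 3, so the condition could fit all of them. The text does not settle this.

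**3. What could it do to attendance?** The plan gives no expected number of non-starters and no expected attendance, so there is no planned figure to reproduce.

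- From the documents: 40 women per group (4.1, 9.1) and the 80% mark (9.4.1, 8.3.3.2).
- Assumed: *k* intervention women never start and attend nothing; each is replaced; starters and replacements attend a mean share *a* of sessions; the 80% mark is a group mean. The plan does not say whether it is a group mean or a threshold for each woman.

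Formulas:

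- Women randomised only: *a*(40 − *k*)/40
- All counted, non-starters and replacements: 40*a*/(40 + *k*)
- Replacements substituted and non-starters dropped: *a*

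For *a* = 0.85 and *k* = 4: 0.85 × 36/40 = 76.50%; 0.85 × 40/44 = 77.27%; 85.00%.

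| *a* | *k* | Randomised | All counted | Substituted |
|---|---|---|---|---|
| 85% | 2 | 80.75% | 80.95% | 85.00% |
| 85% | 3 | 78.63% | 79.07% | 85.00% |
| 85% | 4 | 76.50% | 77.27% | 85.00% |
| 85% | 6 | 72.25% | 73.91% | 85.00% |
| 90% | 4 | 81.00% | 81.82% | 90.00% |
| 90% | 5 | 78.75% | 80.00% | 90.00% |

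With all counted, the gap from the randomised figure is 0.77 points at *a* = 85%, *k* = 4, and 1.66 points at *k* = 6.

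**4. When would the 80% mark be masked?** Under substitution, the reported figure is at or above 80% while the randomised figure is below it only if 80% ≤ *a* < 32/(40 − *k*). The upper limit is 32/39 = 82.1% for *k* = 1, 32/38 = 84.2% for *k* = 2, and 32/36 = 88.9% for *k* = 4. Below 80%, every rule shows a shortfall; at or above the upper limit, none does. With all counted, masking needs *a* of at least 0.80(40 + *k*)/40, which is 88.0% for *k* = 4. That leaves only 88.0% to 88.9%.

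**5. Retention.** Suppose that all 4 non-starters are also lost, along with 10% of everyone else (assumed). Over both arms:

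- Randomised: (0.9 × 36 + 36)/80 = 85.5%
- All counted: 72/84 = 85.7%
- Substituted: 72/80 = 90.0%

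If non-starters are followed like the others, retention is 90.0% under each rule.

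**The case against.** The strongest reply is that section 9.3 already answers the counting question. It sits in the general populations section, covers all subjects, and on its plain words keeps a non-starter in her arm. Because the church is the unit randomised, a replacement can be said to take that church's assignment. That is the all-counted case, where the distortion is small. This stands.

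A reader might infer that section 7.2 will lift reported attendance from 76.5% to 85.0% and switch off the 80% trigger. The documents do not support that. It requires non-starters to be dropped, which no section plans and 9.3 points against. It also needs a particular combination of non-starters and starter attendance: at 85% with 2 non-starters, or 90% with 4, the randomised figure is still above 80%. The trigger is an operational check on data collected weekly and reviewed quarterly, and absentees are contacted by other routes too (5.5, 6.1.1). Attendance and enrolment logs are kept, so any denominator could be rebuilt.

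A reader might also infer inflated retention, a biased efficacy result, or an effect confined to the intervention arm. Visits take place at home (5.5), so not starting classes is not itself loss to follow-up (7.3). Efficacy bias cannot be sized from the documents, and the pilot is not expected to test the main trial's hypotheses (9.1). The one-arm reading is sensible but is not stated.

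None of this touches the main point. Literal intent-to-treat governs who is analysed once enrolled. It cannot undo recruitment into a known arm.

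**Conclusion.** The point holds as a defect in the replacement rule. Section 7.2 permits entry after allocation, with no concealment from recruiters, in a design that otherwise enrols before it randomises. The rule sits badly with analysis by initial randomised assignment. That conclusion rests on the text of 2.3.1, 6.3, 7.2 and 9.3 alone.

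The numerical consequence is conditional and probably small. Replacement is optional and the number of non-starters is unknown. Under the literal reading of 9.3, attendance moves by under 1 point in the main illustration (76.5% against 77.3%, both below the mark). The 85.0% figure arises only under substitution. All of these figures assume the stated *k* and *a* and a group-mean reading of the 80% mark. Missing denominators on their own would be a point of detail; the rule in 7.2 is what makes a change worthwhile. It is a cheap improvement and not a threat to the pilot.

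**What to change.** - **7.2:** delete the sentence allowing replacement after randomisation. Replacement would then be possible only before the churches are randomised.
- **9.3:** state that every woman enrolled at randomisation stays in the intent-to-treat set and in the retention denominator, and that an intervention woman who attends no session stays in the attendance denominator with zero attendance.
- **9.3:** state that any replacement already made is flagged and reported separately, and adjust the reference to all subjects to match.

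A lighter option would keep the replacement rule and add only the counting sentence. That settles the denominators but leaves entry after allocation in place.

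The cost is text only, with no new data. The downside is slightly fewer women in the classes and possibly lower reported attendance.
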